Baseline characteristics of women are age (years), body mass index, parity, current smoker, days of bleeding, length of cycle (days), number of days of heavy bleeding, number of days of painful bleeding, unable to leave house on heaviest days, number of days housebound, number of nights disturbed, Pictorial Bleeding Assessment Chart (PBAC) score (A monthly score of 100 or more on this chart is significantly associated with heavy menstrual bleeding of more than 80 ml per cycle, as measured by the alkaline haematin method), endometrial thickness at time of treatment (mm), uterine size (length x width).

The Exclusion criteria are

1. ultrasound abnormalities (submucosal fibroids, intramural fibroids greater than 3 cm in diameter, large subserosal fibroids, endometrial polyps);
2. laboratory abnormalities (follicle stimulating hormone level higher than 40 iu/l, adverse endometrial histology)
3. hysteroscopic abnormalities (submucosal fibroids, endometrial polyps),
4. incidental adnexal abnormality on ultrasound,
5. severe intermenstrual bleeding, severe dysmenorrhoea, severe premenstrual pain, chronic pelvic pain,
6. medical contraindications to either study treatment,
7. previous endometrial ablation or resection,
8. uninvestigated postcoital bleeding
9. untreated abnormal cervical cytology.

10. pregnancy; lactation; occurrence of <3 menstrual cycles following childbirth, abortion or lactation;
11. current use of an intrauterine device; hypersensitivity to any of the study drug ingredients and known or suspected malignant or premalignant disease.
12. systemic diseases like hypertension, diabetes, thyroid diseases or coronary artery diseases; and history of previous medication for menorrhagia
13. using anticoagulant drugs

Women who were recruited the study will be assessed at 1,3 and 6 months with Hot Flush Rating Scale (HFRS), Menopause Rating Scale (MRS), menorrhagia multi-attribute scale (MM-AS), pictorial bleeding assessment chart and blood sample analysis.

The primary outcomes assessed

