1. Hot flush rating scale: Measures included the HFRS, a self-report measure of frequency and problem rating of Hot Flushes/Night Sweats over the past week. Problem rating is calculated as the mean of the scores on three ten-point scales assessing the extent to which Hot Flushes/Night Sweats are problematic, distressing and causing interference in daily life. Scores for the problem rating range between 1 and 10, with higher scores indicating more problematic Hot Flushes/Night Sweats. The HFRS has been found to have reasonable test–retest reliability and good concurrent validity.
2. Menopause rating scale: The Menopause Rating Scale (MRS) is a questionnaire that assesses the presence and intensity of 11 menopausal symptoms. These are grouped into three subscales: the somatic subscale: assessing hot flushes/sweating, heart discomfort, sleeping problems, and muscle and joint discomfort (items 1–3 and 4 respectively); the psychological subscale: assessing depressive mood, irritability, anxiety, and physical and mental exhaustion (items 4–7 respectively); and the urogenital subscale: assessing sexual problems, bladder problems and vaginal dryness (items 8– 10, respectively). Each of the 11 items can be rated by the participant

from 0 (not present) to 4 (1 ¼ mild, 2 ¼ moderate, 3 ¼ severe and 4 ¼ very severe). The scores obtained for each individual item are summed to provide the corresponding total subscale score. The sum of subscales scores provide the total MRS score. Higher scores are indicative of more severe symptoms. Indeed values above 8 (somatic), 6 (psychological), 3 (urogenital) and 16 (total MRS) were defined as severe.

The secondary outcomes assessed

1. Quality of life as measured by menorrhagia multi-attribute scale: which is designed to measure the effect of menorrhagia on six domains of daily life (practical difficulties, social life, psychological health, physical health, work and daily routine, and family life and relationships). Summary scores, which range from 0 (severely affected) to 100 (not affected)
2. Menstruation, by pictorial bleeding assessment chart
3. Haemoglobin levels were also measured at pre-treatment, 1, 3 and 6 months.
4. Adverse event (Breast pain, Headache, Acne, Alopecia, Migraine, Increase in body weight...)

Statistical analysis

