Data analysis was performed by using SPSS (IBM SPSS Statistics for Windows, Version 20.0. Armonk, NY: IBM Corp.). A one-sample Kolmogorov–Smirnov test was performed to analyze the distribution of clinical variables. The frequency and percentage of the categorical variables and the mean, standard deviation of the continuous and ordinal variables were presented. The study groups were compared using One-way analysis of variance (ANOVA) test for parametric variables and the Kruskal Wallis H test for the non-parametric variables. Wilcoxon signed rank test was used for the comparison of the BAI and FSFI scores at the first visit and second visits. For all calculations, a p-value of <0.05 was considered statistically significant.

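### The only within-patient test is assigned to two scales (BAI and FSFI) that the trial does not list, and no analysis of change over time is specified for the primary outcomes HFRS and MRS

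*Combined protocol and SAP*

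**What the plan says.** The Statistical analysis section contains three comparative tests. Two are for independent groups: "The study groups were compared using One-way analysis of variance (ANOVA) test for parametric variables and the Kruskal Wallis H test", the latter for non-parametric variables. The third is the only paired test: "Wilcoxon signed rank test was used for the comparison of the BAI and FSFI scores at the first visit and second visits". A one-sample Kolmogorov–Smirnov "test was performed to analyze the distribution of clinical variables"; it checks distributions and compares nothing.

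The follow-up sentence after the exclusion criteria says that women "will be assessed at 1,3 and 6 months with Hot Flush Rating Scale (HFRS), Menopause Rating Scale (MRS"), and goes on to MM-AS, the bleeding chart and blood samples. The primary outcomes are HFRS and MRS. The secondary outcomes are MM-AS, PBAC, haemoglobin and adverse events.

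Two outcomes have a documented pre-treatment value. PBAC is in the list of baseline characteristics ("number of nights disturbed, Pictorial Bleeding Assessment Chart (PBAC) score"), and for haemoglobin the secondary outcomes state: "Haemoglobin levels were also measured at pre-treatment, 1, 3 and 6 months".

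**The concern.** A paired test has to name a variable that the trial measures and two visits that the trial schedules. This one does neither in terms that can be matched to the rest of the document. An analyst who follows it literally produces nothing on a listed outcome. An analyst who substitutes HFRS and MRS must choose the score and the pair of visits unaided, and a reader could not tell which choice was planned.

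The baseline question adds to this. The opening section describes recruitment into three groups and mentions no randomisation. If HFRS and MRS were not scored before treatment, change from baseline cannot be reported, and a difference between groups after treatment could reflect different starting scores. Scores not taken before treatment cannot be recovered for women already treated.

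**Working it through.** The plan states no figure for this point, so the check sets its sections side by side and counts.

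**Scales in the paired test against what the trial lists**

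| Source | Items | BAI or FSFI? |
|---|---|---|
| Baseline characteristics | demographic, bleeding, PBAC and uterine items | no |
| Assessments at 1, 3 and 6 months | HFRS, MRS, MM-AS, PBAC, blood samples | no |
| Primary outcomes | HFRS, MRS | no |
| Secondary outcomes | MM-AS, PBAC, haemoglobin, adverse events | no |
| Statistical analysis | BAI, FSFI (not spelled out) | only here |

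- Scales in the paired test that are listed anywhere else: 0 of 2.
- Listed outcomes: 2 primary + 4 secondary = 6. Named in any test sentence: 0 of 6.
- Primary outcomes with a specified within-patient or longitudinal analysis: 0 of 2.

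**Visits.** The test uses two visits, labelled only by their order. The schedule has three follow-ups, or four time points for an outcome also measured before treatment. If HFRS and MRS were substituted, the possible pairs would be:

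- follow-ups only: C(3,2) = 3;
- with a pre-treatment score: C(4,2) = 6.

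The text does not identify one of them.

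**What the between-group sentence leaves open.** The HFRS item reads: "Measures included the HFRS, a self-report measure of frequency and problem rating of Hot Flushes/Night Sweats over the past week". That is two scores. The MRS item describes a total and three subscales, which is four.

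- One score per primary scale: 2 scores × 3 visits = 6 comparisons.
- Every component counted: (2 + 4) scores × 3 visits = 18 comparisons.

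The plan lists HFRS and MRS as primary without saying whether each component is primary, so the count is 6 to 18.

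**Pre-treatment values**

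| Outcome | Pre-treatment value |
|---|---|
| PBAC | documented (baseline characteristics) |
| Haemoglobin | documented (secondary outcomes) |
| HFRS, MRS, MM-AS | not stated; the word *also* in the haemoglobin item could imply one |

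**The case against.** The strongest reply is that this is a comparative study of three groups, so its main analysis is ANOVA or Kruskal Wallis, and a wrong scale name in a supporting paired test leaves that untouched. This stands in part. The between-group comparison survives, and a reader who inferred that the primary outcomes have no analysis at all would go too far. But the surviving sentence names no score or visit, and it does not say whether change or baseline is used.

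Other replies also hold:

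- **The plan assigns tests by type of variable.** That no outcome is named is literally true, but outcomes are covered generically. Adverse events ("Adverse event (Breast pain, Headache, Acne, Alopecia, Migraine" and others) are arguably served already by the stated frequencies and percentages.
- **The visit wording is ambiguous.** A reader might infer that month 6 is left out, taking the two visits as the initial assessment and month 1, or months 1 and 3. The irregular plural also allows a comparison of before with follow-up, which could include month 6. The documents show ambiguity, not exclusion.
- **The loss of baseline is conditional.** It is tempting to conclude that HFRS and MRS have no baseline. The documents leave this open, so it is a question for the sponsor.

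Two further inferences lack support. One is that BAI and FSFI were never collected, or that the sentence came from another study: the documents show only that the scales are unlisted. The other is an inflated false-positive rate from the 6 to 18 comparisons: the count shows what is unspecified, and no error rate follows from it.

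**Conclusion.** The point holds. The plan's only within-patient test is assigned to two unlisted scales at visits that do not match the schedule. As written, it gives a result on 0 of the 6 listed outcomes, and change over time in HFRS and MRS has no specified analysis. The group comparison on both remains possible, with 6 to 18 score-by-visit versions left open.

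This is an error in the working text of the analysis plan, not merely a missing detail, and it is cheap to correct. The conclusion rests on the text alone: the sentence is complete and shows no redaction. It assumes nothing about how the error arose, about sample size or power (the documents give neither), or about whether pre-treatment questionnaires exist.

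**What to change.** The sponsor first confirms two things:

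1. Whether BAI and FSFI belong to this trial. If so, they are listed as secondary outcomes with their visits; if not, they are deleted.
2. Whether pre-treatment HFRS, MRS and MM-AS scores exist.

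The paired-test sentence is then replaced by:

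> HFRS problem rating and MRS total are compared between the three groups at month 6 (the last scheduled visit). Where a pre-treatment score exists, the comparison uses analysis of covariance with that score as covariate or, if the distribution check rejects normality, Kruskal Wallis on change from pre-treatment. Months 1 and 3, the other scores, MM-AS, PBAC and haemoglobin are secondary, with pre-treatment PBAC and haemoglobin as baseline. Within-group Wilcoxon signed rank tests of pre-treatment against month 6 on HFRS, MRS, MM-AS, PBAC and haemoglobin, where a pre-treatment value exists, are supportive.

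Analysis of covariance is named because neither one-way ANOVA nor Kruskal Wallis can adjust for a baseline score.

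The sponsor may name a different score or visit, provided that it is fixed before outcome data are examined. The Statistical analysis section is in the past tense while the follow-up sentence is in the future, so the documents do not settle whether data have been seen. If they have, the choice is labelled post hoc.

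If no pre-treatment HFRS or MRS exists, no change from baseline is claimed for that scale. Its group comparison at month 6 uses the plan's own ANOVA or Kruskal Wallis, with the caution that no randomisation is described and starting scores may differ.

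The cost is two confirmations and a few sentences. The 0.05 level is unchanged. The downside is that fewer comparisons can be presented as primary.

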Date: 01.01.2020

The Effect of Estradiol Valerate, Lng-IUD, and Micronized Progesterone Treatment On Health Quality of Patients with Heavy Menstrual Bleeding

Women who were admitted and treated for heavy menstrual bleeding were asked to participate in this comparative study. Women were eligible for entry if they had self-described heavy menstrual bleeding, had a regular cycle, had completed their family and were 40–50 years old at initial assessment.

After a thorough physical examination and ultrasonographic evaluation, all women underwent endometrial biopsy before the study by using a Pipelle endometrial suction curette to rule out any organic endometrial pathology. Blood samples were analysed to test for hemoglobin (Hb), hematocrit (Hct), ferritin, serum iron and iron-binding capacity and coagulation tests such as prothrombin time and activated partial thromboplastin time.

The study was approved by the Institutional Review Board and Local Ethics Committee. After they gave written informed consent, patients who fulfilled eligibility criteria were recruited to one of the following 3 groups:

Group 1: Women who were treated with estradiol valerate/dienogest regimen for heavy menstrual bleeding. 28 days of E2V/DNG was administered using a dynamic dosing regimen. (E2V 3 mg on days 1–2, E2V 2 mg/DNG 2 mg on days 3–7, E2V 2 mg/DNG 3 mg on days 8–24, E2V 1 mg on days 25–26 and placebo on days 27–28).

Group 2: Women who were treated with LNG-IUD for heavy menstrual bleeding. LNG-IUD is containing 52 mg levonorgestrel at initial placement and releases 20 microgram levonorgestrel per day. This is approved for 5 years of use by the US FDA for treatment of HMB.

Group 3: Women who were treated with oral Micronized Progesterone 200 mg for heavy menstrual bleeding. Cyclic, luteal-phase administration of progestin remained a widely used but little research treatment strategy for HMB for several decades.

None of the recruited patients were not prescribed oral iron preparations and patients who were symptomatic because of anemia (hb<10 mg/dl) were excluded.

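### Two primary scales with no named score, visit or either/both rule, all judged at p<0.05: the plan does not ensure 5% for the primary claim

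*Combined protocol and SAP*

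**What the plan says.** Under *The primary outcomes assessed*, two scales are listed with no order between them.

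- **HFRS:** "a self-report measure of frequency and problem rating of Hot Flushes/Night Sweats over the past week". That is two scores. Only the problem rating is given a calculation (the mean of three ten-point scales), a range (1 to 10) and a direction.
- **MRS:** three subscales and a total, of which the plan says "The sum of subscales scores provide the total MRS score". That is four scores, none named as primary.

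The follow-up sentence after the exclusion criteria says that women "will be assessed at 1,3 and 6 months with Hot Flush Rating Scale (HFRS), Menopause Rating Scale (MRS" and other measures. No visit is singled out.

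Under *The secondary outcomes assessed*, a baseline measurement is explicit for one variable: "Haemoglobin levels were also measured at pre-treatment, 1, 3 and 6 months". No such statement is made for HFRS or MRS, and neither scale is in the list of baseline characteristics.

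Women are "recruited to one of the following 3 groups". *Statistical analysis* says "The study groups were compared using One-way analysis of variance (ANOVA) test for parametric variables and the Kruskal Wallis H test" for non-parametric variables, and then "For all calculations, a p-value of <0.05 was considered statistically significant". It gives no adjustment, testing order, pairwise procedure or definition of success. The one sentence there that mentions visits is a Wilcoxon signed rank test on BAI and FSFI scores, and neither of these is a listed outcome.

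**The concern.** A per-test threshold of 0.05 protects a primary claim at 5% only if the claim rests on one test, or on several tests that must all succeed. Here there are at least two primary tests, and the rule that turns their results into a claim is not stated. With score, visit and rule all open, they can be chosen after the data are seen. A significant result on one scale at one visit could then be reported as the primary finding although no treatment differs from another.

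A second gap follows from the three-group design. A significant ANOVA or Kruskal-Wallis test says that the groups are not all alike. It does not say which treatments differ, and the plan has no step that would.

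**Working it through.** **Inputs from the documents:** threshold 0.05 per calculation; two primary scales; three visits; three groups. The documents give no sample size, power or overall error rate, so there is no figure of the plan's own to reproduce.

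**Assumed:** correlation between the scales (0 to 0.9) and group size (30 or 50 per group). Both scales cover hot flushes (the MRS description has "the somatic subscale: assessing hot flushes/sweating, heart discomfort, sleeping problems"), so some positive correlation is likely. Independence is therefore an upper illustration.

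**1. Either scale suffices, one score and one visit each.** If the tests are independent:

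1 − (1 − 0.05)² = 1 − 0.9025 = 0.0975.

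Whatever the correlation, the rate cannot exceed 0.05 + 0.05 = 0.10. Simulated three-group tests with no true difference (400,000 trials per setting) give:

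| Correlation between scales | Either scale p<0.05 |
|---|---|
| 0 | 9.7–9.8% |
| 0.3 | 9.5% |
| 0.5 | 9.1% |
| 0.7 | 8.4–8.5% |
| 0.9 | 7.1–7.2% |

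The rate returns to 5% only at correlation 1. Kruskal-Wallis tests on skewed integer scores gave a similar range, 6.9–9.8%.

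**2. Either scale suffices at any of the three visits.** This is 2 × 3 = 6 tests. If they are independent:

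1 − 0.95⁶ = 0.265.

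With the same assumed correlation between scales and between visits, the simulated rate is about 18% at 0.7 and 12% at 0.9.

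**3. Both scales required, one prespecified score and visit each.** If no treatment differs on either scale, both tests are significant in 0.05² = 0.25% of trials at correlation 0, and in about 2.9% at 0.9. The worst case is a true difference on one scale only. The claim is then false exactly when the other scale's test is falsely significant, so its probability is at most 5% (simulated 5.0–5.1%).

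**4. The remedy.** Testing each scale at 0.025 under the either-scale rule gives 1 − 0.975² = 4.94% if independent, 4.67% at correlation 0.5 and 3.68% at 0.9.

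Pairwise comparisons need their own limit. Suppose one group truly differs on both scales. Both three-group tests will then usually pass, and a pair with no true difference remains on each scale. Unadjusted pairwise tests at 0.05 on each scale would give up to about 9.8% false pairwise claims. Holding the pairwise family at 0.025 per scale limits the total to 0.025 + 0.025 = 0.05.

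**5. Power cost.** With an assumed 50 per group and effect size f = 0.25 on both scales, the noncentrality is 0.25² × 150 = 9.375 with 2 and 147 degrees of freedom. Power per scale is 78.0% at 0.05 and 68.6% at 0.025. For at least one scale, if independent, 1 − 0.220² = 95% falls to 1 − 0.314² = 90%. At correlation 0.9 it falls from 84% to 75%. Requiring both scales at 0.05 has power of 61% if independent and 72% at 0.9.

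**The case against.** The strongest reply is that the plan never promises 5% across outcomes. It states a threshold per calculation, and it contains no hypothesis or success criterion. The percentages need an either-scale rule that is not written down. If the investigators meant both scales to be required, there is no inflation at a fixed score and visit. This stands, and it is why the figures are conditional. It does not remove the defect: no passage states the both-scales rule, and even under that rule the score and visit would still have to be fixed.

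A reader might infer that the trial's false-positive rate is 7% to 9.75%, or 26.5%. The documents do not support that, because no success rule is stated and the correlations are assumed.

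A reader might also count all (2 + 4) × 3 = 18 score-by-visit results and quote 1 − 0.95¹⁸ = 60%. That treats the results as independent, which cannot hold when the MRS total is the sum of its subscales. Nor do the documents say that any one of the 18 would count.

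Two further points are fair. The HFRS scores are not equally open, since only the problem rating has a stated calculation and range; that makes it the better-specified score but does not designate it. And with no randomisation described, controlling chance findings would not by itself make a group difference attributable to treatment.

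**Conclusion.** The concern holds in conditional form and should be fixed. The primary score, visit and success rule are undefined, and the blanket 0.05 does not ensure 5% for the primary claim. The excess depends on the missing rule: a rate of about 7–9.75% if either scale suffices at one score and visit, about 12–26.5% if any visit counts, and at most 5% if both scales are required at one prespecified score and visit. The ranges rest on assumed correlations of 0.9 to 0, and the simulations on assumed group sizes. They cover chance findings only.

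It would go too far to infer that HFRS and MRS were not measured before treatment. The documents are silent on this, so whether change can be analysed is unknown. Nor does the BAI and FSFI sentence settle a primary visit, since it concerns scales that are not listed outcomes.

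**What to change.** Before analysis, amend the SAP as follows.

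1. **Name one score and one visit per scale.** The HFRS problem rating is the better-specified HFRS score. The documents do not choose an MRS score or a visit, so the sponsor must.
2. **State the success rule and replace the blanket 0.05 for the primary outcomes.** Either (A) one scale suffices and each scale's three-group test is run at 0.025, or (B) both scales are required and each is tested at 0.05.
3. **Follow a significant result (under B, both results) with pairwise comparisons.** Use one adjusted method for both tests and intervals, at 0.025 per scale: for example Tukey, or Bonferroni-adjusted rank comparisons where Kruskal-Wallis is used (0.025/3 = 0.0083 per pair, so 99.17% intervals).
4. **State what is analysed.** Use the visit value unless pre-treatment HFRS and MRS were collected; only then use change or baseline adjustment.
5. **Correct the BAI and FSFI sentence** so that it refers to listed outcomes, or remove it.
6. **Reconcile the MRS item numbering before scoring.** Item 4 is placed in two subscales, and the numbering stops at 10 although there are 11 items.
7. **Label all other scores, visits and the secondary outcomes as supportive.**

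The cost is mostly wording and some power: under (A), 78% to 69% per scale in the assumed setting of 50 per group and f = 0.25. Another score or visit can no longer be claimed as primary. If pre-treatment scores were not collected, change from baseline is not available by rewording the SAP. Bias from allocation needs separate treatment.
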